**Dose escalation schedules are as follows:**

Dose level	Clofarabine (mg/m^2 IV daiy for 5 days)
-1	10
1 Starting	15
2	20
3	25
4	30

A DLT is defined as a clinically significant adverse event or abnormal laboratory value assessed as unrelated to disease progression, intercurrent illness, or concomitant medications and occurring during the first course on study that meets any of the following criteria:

- CTCAE Grade 3 AST (SGOT) or ALT (SGPT) for > 7 days
- CTCAE Grade 4 AST (SGOT) or ALT (SGPT) of any duration
- All other clinically significant NCI common terminology criteria that are CTCAE Grade 3 or 4

An AE must be clinically significant to define DLT e.g. alopecia, study drug-related fever, electrolyte abnormalities (including K, Na, Cl, HCO3, Mg, Ca) that are < Grade 3 will not define the DLT. Drug-related Grade 3-4 nausea and vomiting not controlled with adequate therapy and Grade 3-4 hyperbilirubinemia will be considered DLTs. Only prolonged myelosuppression, as defined by the NCI criteria specific for leukemia, i.e. marrow cellularity <5% on day 42 or later (6 weeks) from start of therapy without evidence of leukemia, will be considered in defining the MTD and DLT.

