**2. Induction**

**2.1 Phase I (fixed dose of idarubicin of 10 mg/m^2 day 1-3 and cytarabine 1 g/m^2 day 1-5)**

Clofarabine IV over approximately 1 hour daily for 5 days (days 1-5). Dose levels and dose escalation schema are described below.

Idarubicin 10 mg/m^2 IV over approximately 30 minutes daily for 3 days (days 1-3)

Cytarabine 1 g/m^2 IV over approximately 2 hours daily for 5 days (days 1-5)

Idarubicin will follow clofarabine by 1 to 2 hours and cytarabine will follow clofarabine by 3 to 6 hours. All chemotherapeutic agents will be dosed, prepared, and administered according to MDACC institutional guidelines. BSA will be recalculated prior to each subsequent course.

Patients will be entered sequentially to each dose level. If none of the first 3 patients at a dose level experience first cycle dose-limiting toxicity (DLT), new patients may be entered at the next higher dose level. If 1 of 3 patients experience first cycle DLT, up to 3 more patients are started at that same dose level. If 2 or more experience first cycle DLT, no further patients are started at that dose and clofarabine's dose will be reduced to -1 level, which is 10 mg/m^2 IV daily for 5 days. The MTD is the highest dose level in which <2 patients of 6 develop first cycle DLT. New dose levels may begin accrual only if all patients at the current dose level have been observed for a minimum of 4 weeks.

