## 2.2 Phase II

In the Phase II portion, patients will randomized to receive

a. Clofarabine (dose selected based on Phase I portion) IV over approximately 1 hour daily for 5 days (days 1-5)

b. Idarubicin  $10 \text{ mg/m}^2$  IV over approximately 30 minutes daily for 3 days (days 1-3)

c. Cytarabine  $1 \text{ g/m}^2$  IV over approximately 2 hours daily for 5 days (days 1-5)

Idarubicin will follow clofarabine by 1 to 2 hours and cytarabine will follow clofarabine by 3 to 6 hours.

**or**

a. Fludarabine  $30 \text{ mg/m}^2$  IV over approximately 30 minutes daily for 5 days (days 1-5)

b. Idarubicin  $10 \text{ mg/m}^2$  IV over approximately 30 minutes daily for 3 days (days 1-3)

c. Cytarabine  $1 \text{ g/m}^2$  IV over approximately 2 hours daily for 5 days (days 1-5)

Idarubicin will follow fludarabine by 1 to 2 hours and cytarabine will follow fludarabine by 3 to 6 hours.

The induction or reinduction may be given over 4 days (Fludarabine, Clofarabine and Cytarabine) in patients  $\geq 65$  years, or at the discretion of the treating physician and over 3 days (Fludarabine, Clofarabine and Cytarabine) in patients with PS  $\geq 2$ , or at the discretion of the treating physician. Idarubicin  $8\text{-}10 \text{ mg/m}^2$  will be given for 2 days in these situations.

Patients, who have not achieved a complete remission following one induction course can receive a second induction course to optimize response if possible. A second induction course at the same dose as the previous course or in a dose-reduced fashion

should not be given until at least 28 days of course 1. If the bone marrow aspirate and/or biopsy(s) performed after the re-induction cycle reveals a remission marrow (CR/CRp), then the patient may proceed with consolidation at the discretion of the treating investigator. In addition, any clinically significant drug-related, non-hematologic toxicity experienced by a patient should return to  $\leq$  grade 2 or the baseline grade before the patient continues treatment. Should the patient not have achieved a remission after the reinduction course, he will be taken off study for failure to respond, unless the patient has achieved clinical benefit or partial remission, at which time further therapy on protocol may be permitted with approval from the PI.

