### **Consolidation**

Patients in CR or CRp can continue with up to 6 consolidation cycles.

Clofarabine (dose selected based on Phase I portion) IV over approximately 1 hour daily for 3 days (days 1-3)

Idarubicin 8 mg/m^2 IV over approximately 30 minutes daily for 2 days (days 1-2)

Cytarabine 1 g/m^2 IV over approximately 2 hours daily for 3 days (days 1-3)Or

Fludarabine 30 mg/m^2 IV over approximately 30 minutes daily for 3 days (days 1-3)

Idarubicin 8 mg/m^2 IV over approximately 30 minutes daily for 2 days (days 1-2)

Cytarabine 1 g/m^2 IV over approximately 2 hours daily for 3 days (days 1-3)

The consolidation may be given over 2 days in patients  $\geq$  65 years and/or with PS  $\geq$  2.

Cycles may be repeated every 3 to 10 weeks based on leukemia response and resolution of drug-related toxicities. Prior to each consolidation cycle, the ANC should be  $\geq 1.0 \times 10^9/L$ , and the platelet count should be  $\geq 60 \times 10^9/L$  (except for patients who are considered to have achieved a CRp following induction/reinduction and in whom the platelet count may be lower). Patients with borderline values for ANC and platelet count (value up to 10% lower than recommended) can still proceed with the next consolidation cycle if this is judged to be in the best interest of the patients and after discussion with the principal investigator. In addition, any drug-related non-hematologic toxicity experienced by the patient must return to  $\leq$  grade 2 before receiving the next cycle. Doses missed or held during a cycle of treatment will not be made up and are recorded as being omitted. If patients experience multiple study drug-related toxicities or experience significant infections, dose adjustments may need to be made based on the most severe toxicity and based on the drug causing the toxicity.

Dose modifications:

Drug doses in subsequent consolidation cycles may be modified for drug-related  $>$  grade 2 non-hematologic toxicities. Dose reductions can also be made in other clinical situations where this step is considered to be in the best interest for the patient and after discussion with the principal investigator. The following table is a suggestion for dose modifications in subsequent treatment courses:

Dose level	Fludarabine (mg/m  )	Clofarabine (mg/m  )	Idarubicin (mg/m  )	Cytarabine (g/m  )
-1	22.5	15	8	0.75
-2	20	15	6	0.5

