### During Therapy

Procedure	Comments	Schedule
Hematology	CBC with differential and platelet count	Every 3-7 days (the differential may be omitted when WBC is $\leq 500$ )
Biochemistry	Creatinine, total bilirubin, SGPT or SGOT	Once weekly
Physical Examination	Focused physical examination	Prior to each treatment course
Bone marrow	Aspirate and/or biopsy	On day 28 +/- 7 days

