### **Phase II**

The phase II portion of the study will include only newly diagnostic AML patients, and the primary objective is to compare the event-free survival (EFS) between treatment CIA and FLAI, where event is defined as be resistance to treatment, relapse (after response) or death, whichever occurred first.

A maximum of 200 front-line patients will be enrolled in the study. To enroll 200 front line patients, the total sample size (front-line and salvage patients combined) is 280.

This section will focus on front-line patients only. An adaptive randomization algorithm will be used to assign the patients to the two treatment arms. Initially 40 patients will be randomized equally to the two treatment arms. After the completion of the equal randomization, the adaptive randomization algorithm will be employed to unbalance the

randomization probabilities in favor of the treatment arm with a better event free survival. The expected accrual rate is about 5 patients per month, and the additional follow-up time is 12 months after all patients have been enrolled to the study.

The historical data suggested the median event free survival time for FLAI treatment was 5 months. Let  $\theta_1$  and  $\theta_2$  denote the median event free survival time for treatment arm CIA and FLAI respectively, we assume the prior for the median event free survival time follows Inverse Gamma (IG) distribution:  $\theta_1 \sim \text{IG}(3, 10)$ , and  $\theta_2 \sim \text{IG}(3, 10)$ . Each time a new patient enters the trial, be the posterior probabilities  $\pi_i = \Pr(\theta_i > \theta_j \mid \text{data})$  will be calculated ( $i, j = 1, 2$ ). The randomization probability to treatment arm CIA and FLAI will be the posterior probabilities  $\pi_i = \frac{\sqrt{\pi_i}}{\sqrt{\pi_1} + \sqrt{\pi_2}}$ .

The trial will be stopped early for both efficacy and futility based on the follow stopping rules. Table 1 presents the operating characteristics of simulations based on the described design.

1. Early loser selection: Suspend accrual to an arm  $i$  if  $\Pr(\theta_i < \theta_{j \neq i} \mid \text{Data}) < 0.025$
2. Early winner selection: Stop the trial and select an arm  $i$  as superior if  $\Pr(\theta_i > \theta_{j \neq i} \mid \text{Data}) > 0.975$
- 3 Final winner selection: At the final analysis after all patients have been evaluated, select arm  $i$  as superior if  $\Pr(\theta_i > \theta_{j \neq i} \mid \text{Data}) > 0.975$

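### The phase I rule permits clofarabine escalation up to 14 days before the only myelosuppression DLT can be assessed in the last patient at the level below

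*Combined protocol and SAP*

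**What the plan says.** The DLT definition, which follows the dose-level table in section 2.1, covers clinically significant events "occurring during the first course on study that meets any of the following criteria". It then restricts myelosuppression to one form: "marrow cellularity <5% on day 42 or later (6 weeks) from start of therapy without evidence of leukemia". Earlier cytopenia does not count.

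The escalation rule in section 2.1 is a 3+3. A level with no first-cycle DLT in three patients may be followed by the next level, subject to this condition: "New dose levels may begin accrual only if all patients at the current dose level have been observed for a minimum of 4 weeks". The MTD is defined in the same section: "The MTD is the highest dose level in which <2 patients of 6 develop first cycle DLT".

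Four other places bear on timing:
- The During Therapy table in section V dates the marrow as "On day 28 +/- 7 days". The list above that table also asks for a marrow aspirate to confirm remission, without a date, and for blood counts every 3 to 7 days.
- Section 2.2, which is phase II text, says a second induction "should not be given until at least 28 days of course 1".
- The Consolidation section sets a count threshold: "Prior to each consolidation cycle, the ANC should be" at least 1.0 x 10^9/L, with platelets at least 60 x 10^9/L. It excepts patients classed as CRp, whose platelets may be lower.
- Section X, Phase I, refers back to section 2.1 for the escalation rules and caps phase I at 24 patients.

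**The concern.** The protocol names prolonged aplasia as a DLT but lets the escalation decision be taken before that DLT can exist. At day 28 a leukemia-free patient with an empty marrow has no DLT under the definition, and the cohort can be read as 0 of 3. New patients may then start a higher clofarabine dose while that patient is still on the way to becoming a DLT.

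Marrow toxicity is a natural worry for this regimen. The Rationale reports an earlier recommended combination with clofarabine 22.5 mg/m2 and idarubicin 6 mg/m2. This trial fixes idarubicin at 10 mg/m2 and takes clofarabine to 25 and 30 mg/m2 at levels 3 and 4.

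Two further gaps sit beside the first. The 4-week condition speaks only of opening new dose levels, so no wait is stated before the MTD is declared and phase II begins. Nor does the plan say what happens to patients already at the higher level if a late DLT appears below.

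**Working it through.** **Inputs.** Day 42 (DLT definition, section 2.1); minimum 4 weeks (escalation rule, section 2.1); marrow at day 28 +/- 7 (section V); four dose levels plus level -1 (section 2.1); phase I cap of 24 (section X). The documents give no rate of day-42 aplasia and no phase I accrual rate.

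**The plan's own figures.** 6 weeks x 7 = 42 days, as stated. 4 levels x 6 patients = 24, which matches the cap.

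**The gap.** 4 x 7 = 28 days, and 42 - 28 = 14 days for the last patient entered at a level. It is 13 days if treatment starts on day 1 and the level opens on day 29 (42 - 29). It is shorter for patients entered earlier. The scheduled marrow window is days 21 to 35, so it closes 42 - 35 = 7 days before the criterion can be met.

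**Does other text close it?** The words cycle and course might imply a longer wait, but no section gives a phase I cycle length. The nearest text is the phase II statement on second induction, and it points to 28 days. Section X adds nothing to section 2.1. No day-42 marrow is scheduled, and no section makes escalation wait for recovery.

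**How many patients could be in the gap?** The only accrual figure is for phase II: "The expected accrual rate is about 5 patients per month". Using it for phase I is an assumption. With even spacing and 30.44 days per month, when the third patient reaches day 28:
- 5 per month: entries 6.1 days apart; patients at days 40.2, 34.1 and 28.0; all three in the gap. In 14 days, 14 x 5/30.44 = 2.3 patients could start the next level.
- 4 per month: days 43.2, 35.6 and 28.0; two in the gap.
- 3 per month: days 48.3, 38.1 and 28.0; two in the gap.
- 2 per month: days 58.4, 43.2 and 28.0; one in the gap; 14 x 2/30.44 = 0.9 patients could start the next level.

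**Chance of a late DLT (illustration only).** Let b be the chance that a patient in the gap, DLT-free at day 28, goes on to meet the day-42 criterion. With k patients in the gap, P(at least one) = 1 - (1 - b)^k.
- k = 1: equal to b, so 0 to 0.30 for b from 0 to 0.30.
- k = 3: 0 at b = 0; 0.143 at 0.05; 0.271 at 0.10; 0.488 at 0.20; 0.657 at 0.30.
- Two or more of three: 0.007, 0.028, 0.104 and 0.216 at b = 0.05, 0.10, 0.20 and 0.30.

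**The MTD (a separate question).** A late DLT still counts if it is scored. Suppose instead that day-42 marrows are never done, and assume other DLTs at 10%. The chance of clearing a level (0 of 3, or 1 of 6) is (1 - p)^3 + 3p(1 - p)^5.
- Aplasia unscored, p = 0.10: 0.906.
- Aplasia scored, at 5% or 20%, with the rarer event falling wholly within patients who have the commoner one (p = 0.10 or 0.20): 0.906 or 0.709.
- Aplasia scored, at 5% or 20%, independent of other DLTs (p = 1 - 0.9 x 0.95 = 0.145, or 1 - 0.9 x 0.80 = 0.28): 0.824 or 0.536.

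These figures measure the effect of missing the assessment, not of the 14-day gap.

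**The case against.** The strongest reply is that 4 weeks is a floor. The rule needs both no first-cycle DLT and at least 4 weeks of observation, so an investigator facing an aplastic, leukemia-free patient at day 28 may wait, and the DLT definition gives reason to. The decision is not blind either: frequent blood counts and the day-28 marrow would normally show who is at risk. This stands to the extent that the plan permits early escalation and does not instruct it. It does not remove the point, because the safeguard then rests on discretion and nothing written requires the wait.

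Second, a reader might infer that this is the only hematologic DLT. The documents do not support that. The general Grade 3-4 criterion can take in bleeding, infection and other clinically significant events, so the gap is chiefly aplasia without another DLT.

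Third, a reader might infer that the MTD will be set too high. That does not follow either. Late DLTs count if scored, and where six patients are treated at the MTD level the first three will usually be past day 42 when the last is assessed.

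Fourth, the percentages rest on assumed rates. The 66% figure needs both a 30% aplasia rate and phase II accrual applied to phase I. That objection stands in full.

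**Conclusion.** The timing mismatch is real and follows from the text alone: up to 14 days between the earliest permitted escalation and the earliest time the myelosuppression DLT can be scored in the last patient of a cohort. The consequence is permitted premature escalation, in a phase I of at most 24 patients.

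Its frequency is unknown. The exposure of about 0.9 to 2.3 patients per gap depends on assumed accrual of 2 to 5 per month, and the late-DLT probabilities only show what various aplasia rates would imply. Upward bias in the MTD is conditional on late DLTs not being scored. That possibility is not remote on paper, because no day-42 marrow is scheduled, but the documents do not show that it would happen. The change is worth making because it is a safety matter that a short addition can close. It does not invalidate the design.

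**What to change.** Add to the escalation rule in section 2.1:

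- At 4 weeks, a higher level, or MTD declaration and the start of phase II, may begin only if every patient at the current level without persistent leukemia and without a scored DLT has one of two things: count recovery (ANC at least 1.0 and platelets at least 60 x 10^9/L, keeping the Consolidation section's exception for CRp), or a marrow from the day 28 +/- 7 assessment with cellularity of at least 5%.
- Otherwise, wait until that patient recovers or has the day-42 cellularity assessment that the DLT definition already calls for. Until then the patient is not counted as DLT-free.
- A patient who leaves, dies of another cause or is re-treated before day 42, while unrecovered and without a DLT, is replaced for the DLT count.

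The CRp exception and the marrow alternative keep a patient with slow platelets but a cellular marrow from holding up the trial. The replacement rule prevents an indefinite stall.

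**Cost.** Protocol wording and a conditional hold of up to 14 days per affected cohort. If every step were affected once, that is 3 escalations x 14 = 42 days, or 56 with the step into phase II. A level expanded to six after a late DLT could incur the hold twice, adding 14 days each time. At the phase II accrual rate, 56 days corresponds to 56 x 5/30.44 = 9.2 patients delayed or not enrolled, though the hold applies only when a leukemia-free patient has not recovered. Replacements should occasionally be needed and should stay within the 24-patient cap. That cap leaves no room if all four levels are expanded to six.

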## 2.2 Phase II

In the Phase II portion, patients will randomized to receive

a. Clofarabine (dose selected based on Phase I portion) IV over approximately 1 hour daily for 5 days (days 1-5)

b. Idarubicin  $10 \text{ mg/m}^2$  IV over approximately 30 minutes daily for 3 days (days 1-3)

c. Cytarabine  $1 \text{ g/m}^2$  IV over approximately 2 hours daily for 5 days (days 1-5)

Idarubicin will follow clofarabine by 1 to 2 hours and cytarabine will follow clofarabine by 3 to 6 hours.

**or**

a. Fludarabine  $30 \text{ mg/m}^2$  IV over approximately 30 minutes daily for 5 days (days 1-5)

b. Idarubicin  $10 \text{ mg/m}^2$  IV over approximately 30 minutes daily for 3 days (days 1-3)

c. Cytarabine  $1 \text{ g/m}^2$  IV over approximately 2 hours daily for 5 days (days 1-5)

Idarubicin will follow fludarabine by 1 to 2 hours and cytarabine will follow fludarabine by 3 to 6 hours.

The induction or reinduction may be given over 4 days (Fludarabine, Clofarabine and Cytarabine) in patients  $\geq 65$  years, or at the discretion of the treating physician and over 3 days (Fludarabine, Clofarabine and Cytarabine) in patients with PS  $\geq 2$ , or at the discretion of the treating physician. Idarubicin  $8\text{-}10 \text{ mg/m}^2$  will be given for 2 days in these situations.

Patients, who have not achieved a complete remission following one induction course can receive a second induction course to optimize response if possible. A second induction course at the same dose as the previous course or in a dose-reduced fashion

should not be given until at least 28 days of course 1. If the bone marrow aspirate and/or biopsy(s) performed after the re-induction cycle reveals a remission marrow (CR/CRp), then the patient may proceed with consolidation at the discretion of the treating investigator. In addition, any clinically significant drug-related, non-hematologic toxicity experienced by a patient should return to  $\leq$  grade 2 or the baseline grade before the patient continues treatment. Should the patient not have achieved a remission after the reinduction course, he will be taken off study for failure to respond, unless the patient has achieved clinical benefit or partial remission, at which time further therapy on protocol may be permitted with approval from the PI.

### **Consolidation**

Patients in CR or CRp can continue with up to 6 consolidation cycles.

Clofarabine (dose selected based on Phase I portion) IV over approximately 1 hour daily for 3 days (days 1-3)

Idarubicin 8 mg/m^2 IV over approximately 30 minutes daily for 2 days (days 1-2)

Cytarabine 1 g/m^2 IV over approximately 2 hours daily for 3 days (days 1-3)Or

Fludarabine 30 mg/m^2 IV over approximately 30 minutes daily for 3 days (days 1-3)

Idarubicin 8 mg/m^2 IV over approximately 30 minutes daily for 2 days (days 1-2)

Cytarabine 1 g/m^2 IV over approximately 2 hours daily for 3 days (days 1-3)

The consolidation may be given over 2 days in patients  $\geq$  65 years and/or with PS  $\geq$  2.

Cycles may be repeated every 3 to 10 weeks based on leukemia response and resolution of drug-related toxicities. Prior to each consolidation cycle, the ANC should be  $\geq 1.0 \times 10^9/L$ , and the platelet count should be  $\geq 60 \times 10^9/L$  (except for patients who are considered to have achieved a CRp following induction/reinduction and in whom the platelet count may be lower). Patients with borderline values for ANC and platelet count (value up to 10% lower than recommended) can still proceed with the next consolidation cycle if this is judged to be in the best interest of the patients and after discussion with the principal investigator. In addition, any drug-related non-hematologic toxicity experienced by the patient must return to  $\leq$  grade 2 before receiving the next cycle. Doses missed or held during a cycle of treatment will not be made up and are recorded as being omitted. If patients experience multiple study drug-related toxicities or experience significant infections, dose adjustments may need to be made based on the most severe toxicity and based on the drug causing the toxicity.

Dose modifications:

Drug doses in subsequent consolidation cycles may be modified for drug-related  $>$  grade 2 non-hematologic toxicities. Dose reductions can also be made in other clinical situations where this step is considered to be in the best interest for the patient and after discussion with the principal investigator. The following table is a suggestion for dose modifications in subsequent treatment courses:

Dose level	Fludarabine (mg/m  )	Clofarabine (mg/m  )	Idarubicin (mg/m  )	Cytarabine (g/m  )
-1	22.5	15	8	0.75
-2	20	15	6	0.5

-3	15	10	6	0.25
----	----	----	---	------

Doses of each individual drug can be modified if a toxicity is considered due this particular drug.

Specific Dose Modifications for Organ Function:

	Fludarabine (mg/m  )	Cytarabine (g/m  )	Idarubicin (mg/m  )	Clofarabine (mg/m  )
Creatinine (mg/dL)				
2.1 – 3 (age < 65)	22.5	0.75	10 * 8 **	75% of current dose level
2.1 – 3 (age ≥ 65)	15	0.5	8 * 6 **	50% of current dose level
Above 3	Discuss with study principal investigator			
Bilirubin (mg/dL)				
2.6 – 5	30	1	5 * 4 **	Current dose level
Above 5	30	1	OMIT	Current dose level

\*Induction/Re-Induction

\*\*Consolidation

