**Adverse effects:**

- Cardiovascular: Transient EKG abnormalities (supraventricular tachycardia, S-T wave changes, atrial or ventricular extrasystoles); generally asymptomatic and self-limiting. Congestive heart failure, dose-related. The relative cardiotoxicity of idarubicin compared to doxorubicin is unclear. Some investigators report no increase in cardiac toxicity at cumulative oral idarubicin doses up to 540 mg/m^2; other reports suggest a maximum cumulative intravenous dose of 150 mg/m^2.
- Central nervous system: Headache
- Dermatologic: Alopecia (25% to 30%), radiation recall, skin rash (11%), urticaria
- Gastrointestinal: Nausea, vomiting (30% to 60%); diarrhea (9% to 22%); stomatitis (11%); GI hemorrhage (30%)
- Genitourinary: Discoloration of urine (darker yellow)

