#### **IV. Eligibility criteria**

##### **Inclusion criteria:**

- Sign an IRB-approved informed consent document.
- Age 18 to 60. Patients above the age of 60 only with PI approval
- Diagnosis of newly diagnosed AML [other than acute promyelocytic leukemia (APL)]. Prior therapy with hydrea and the use of a single or a two day dose of cytarabine (up to 3 g/m^2) for emergency use up to 24 hours prior to start of study therapy is allowed. Prior therapy for MDS or other AHD is not allowed.
- ECOG performance status of ≤ 3 at study entry.
- Organ function as defined below (unless due to leukemia):

- Serum creatinine  $\leq 3$  mg/dL
- Total bilirubin  $\leq 2.5$  mg/dL
- ALT (SGPT)  $\leq 3$  x ULN or  $\leq 5$  x ULN if related to disease
- Women of childbearing potential must have a negative serum or urine pregnancy test within 7 days. Men must agree not to father a child and agree to use a condom if his partner is of child bearing potential.
- Cardiac ejection fraction  $\geq 40\%$  (by either cardiac echo or MUGA scan).  
Documentation of recent ( $\leq 6$  months from screening) outside reports is acceptable.

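### The printed schedule permits 156 mg/m² of intravenous idarubicin on study, 6 mg/m² above the maximum that some reports are said to suggest, and no printed rule is triggered by cumulative dose (minor)

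*Combined protocol and SAP*

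**What the plan says.** **Dosing.** In section 2.2 Phase II, both CIA and FLAI give idarubicin 10 mg/m² IV on days 1 to 3. A patient not in complete remission may have one more induction: "A second induction course at the same dose as the previous course or in a dose-reduced fashion". If that produces a remission, the investigator may go on to consolidation. There, "Patients in CR or CRp can continue with up to 6 consolidation cycles", with idarubicin 8 mg/m² IV on days 1 and 2 in both arms.

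**Cardiac background.** Section III.A lists "Congestive heart failure, dose-related" among the adverse effects. It adds that "The relative cardiotoxicity of idarubicin compared to doxorubicin is unclear", that some investigators saw no increase in cardiac toxicity at oral totals up to 540 mg/m², and that "other reports suggest a maximum cumulative intravenous dose of 150 mg/m"².

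**Controls.** The Inclusion criteria require an ejection fraction of at least 40% ("by either cardiac echo or MUGA scan"), and an outside report up to six months old is acceptable. Section 2.1 says "All chemotherapeutic agents will be dosed, prepared, and administered according to MDACC institutional guidelines". The Consolidation section also allows discretion, after discussion with the principal investigator: "Dose reductions can also be made in other clinical situations where this step is considered to be in the best interest for the patient".

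**The concern.** The protocol describes a dose-related cardiac toxicity and cites one cumulative figure for the route used in this trial. It does not set that figure beside its own maximum schedule. A patient who follows the printed doses exactly can pass it without any rule asking anyone to add up the doses.

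The printed triggers for changing idarubicin are observed toxicity, creatinine, bilirubin, age, performance status and clinical judgement. The withdrawal criteria do not mention cumulative dose. The on-treatment evaluations in section V cover blood counts, chemistry, marrow and a focused physical examination, with no repeat ejection fraction. What is at stake is late anthracycline exposure in patients who are in remission, where a reduction could be made but nothing prompts it.

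**Working it through.** The protocol states no cumulative idarubicin total, so there is no printed figure to reproduce.

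**Inputs**
- Full induction (2.2 Phase II): 10 × 3 = 30 mg/m².
- Shortened induction (2.2 Phase II; older patients, poorer performance status or physician's choice): 8 to 10 mg/m² × 2 = 16 to 20 mg/m².
- Full consolidation: 8 × 2 = 16 mg/m².
- Consolidation at 6 mg/m² (suggested dose levels −2 and −3): 6 × 2 = 12 mg/m².
- Benchmark (III.A): 150 mg/m² IV.

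**Maximum path.** 2 × 30 + 6 × 16 = 60 + 96 = 156 mg/m². Excess: 156 − 150 = 6 mg/m²; 156/150 = 1.04.

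**Effect of reduced consolidations.** With two full inductions and k of the six consolidations at 6 mg/m², the total is 60 + 16(6 − k) + 12k:

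| k | 0 | 1 | 2 | 3 | 4 | 5 | 6 |
|---|---|---|---|---|---|---|---|
| Total (mg/m²) | 156 | 152 | 148 | 144 | 140 | 136 | 132 |

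Only k = 0 and k = 1 exceed 150.

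**Other fully specified paths**
- Two full inductions, five consolidations: 60 + 80 = 140.
- One full induction, six consolidations: 30 + 96 = 126.
- Full induction, then shortened re-induction, six consolidations: 30 + 16 to 20 + 96 = 142 to 146.
- Both inductions shortened, six consolidations: 32 to 40 + 96 = 128 to 136.
- Creatinine 2.1–3 mg/dL at age 65 or over throughout: 2 × 8 × 3 + 6 × 6 × 2 = 48 + 72 = 120.
- Full induction, then re-induction at 8 mg/m² × 3, six consolidations: 30 + 24 + 96 = 150, at the figure but not above it. The 8 mg/m² is an assumption taken from dose level −1, because section 2.2 does not size the reduction.

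**Printed adjustments that leave 156 reachable.** Dose level −1 sets idarubicin at 8 mg/m², which is already the consolidation dose. Creatinine 2.1–3 mg/dL below age 65 keeps 10 mg/m² in induction and 8 mg/m² in consolidation. Two-day consolidation does not shorten idarubicin, which is already given on two days.

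**Paths that cannot be totalled.** Section 2.2 allows further therapy with the principal investigator's approval after a failed re-induction, if there is clinical benefit or partial remission. Section VII does the same after relapse with clinical benefit. Neither states a dose or a number of cycles, so these routes could also exceed 150.

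**Timing.** At least 4 weeks separate the two inductions, and five intervals of 3 to 10 weeks separate consolidations 1 and 6 (15 to 50 weeks). Cycle 6 therefore starts at least 4 + 15 = 19 weeks after the first idarubicin dose, before adding the gap between re-induction and consolidation 1.

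**The case against.** The strongest objection is that nothing printed is violated. The 150 mg/m² figure stands in a background list of adverse effects, is attributed to some reports, and sits beside a much higher oral figure and a statement of uncertainty. This stands: a reader might infer that the regimen breaches the protocol's own safety limit, but the protocol sets no such limit. The figure keeps some weight because it is the only intravenous one cited and every idarubicin dose in the trial is intravenous.

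Second, each step to 156 is optional, and doses missed or held are not made up. One missed 8 mg/m² day on the maximum path gives 156 − 8 = 148. This also stands and limits how many patients are affected.

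Third, control does not end at entry. Non-haematological drug toxicity must recover to grade 2 or less before each consolidation cycle, individual drugs can be adjusted, a focused examination precedes each course, and the Toxicity monitoring rule in section X acts on treatment-related non-haematological events of grade 3 or worse. A reader might therefore be wrong to infer that patients are cardiologically unprotected after entry. These controls respond to toxicity once seen, or to judgement; none responds to accumulated dose.

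Fourth, the institutional guidelines are not in the documents and may hold a cap. That confines the point to what is printed.

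A reader might also infer higher totals from anthracycline given before entry, since section X counts salvage patients, or a greater cardiac risk with CIA, since clofarabine's adverse effects also include heart failure. The documents give neither prior doses nor cardiac event rates, so neither inference is made here.

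**Conclusion.** The point holds as a minor, inexpensive improvement. The printed doses permit 156 mg/m² of intravenous idarubicin on study, 4% above a suggested maximum that the protocol cites but does not adopt, and no printed rule is triggered by cumulative dose. Among fully specified paths, only two full inductions followed by six consolidations, with at most one at 6 mg/m², go above 150 (156 or 152). Approved further therapy is a separate, unquantified route.

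The conclusion assumes that doses are given as printed and counts on-study drug only. The documents do not say how many patients would reach these totals; the number is probably small. They do not support calling this a dosing error or a major risk. If the institutional guidelines already cap cumulative idarubicin, what remains is a missing cross-reference.

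**What to change.** Add to the Consolidation section a running-total rule covering all therapy given on protocol: before each cycle, sum the intravenous idarubicin given on study; if the planned cycle would take the total above 150 mg/m², reduce or omit idarubicin in that cycle so that it does not, and continue the other drugs. If the institutional guidelines already set a cumulative cap, apply and cite that cap instead.

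On the maximum path the total before cycle 6 is 140. Cycle 6 would then carry no idarubicin (140) or a single 8 mg/m² day (148). Giving 6 mg/m² on both days is not enough (140 + 12 = 152). A running total is better than a fixed limit of five full cycles after two full inductions. It leaves cycle 6 intact for a patient with two earlier cycles at 6 mg/m² (132 + 16 = 148), and it also covers the approved further therapy whose dose is not stated.

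The cost is a short addition to the text and a sum from dosing records, with no new test. The clinical downside on the maximum path is 8 to 16 mg/m² less idarubicin in one late cycle, for a probably small number of patients.
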